7.11.3 Vital Signs

Vital signs' (including pulse rate, weight, SBP, DBP, body temperature and respiratory rate) collection schedule is presented in [Table 4.c](#), and baseline, postdose, and changes from baseline to each post-dose values will be summarized using descriptive statistics by visit and regimen for each part.

Number and percentage of subjects with markedly abnormal value (MAV) will also be tabulated based on the criteria listed in [Appendix B](#).

All vital signs data will be presented in the listings.

7.11.4 12-Lead ECGs

ECG data collection schedule is presented in [Table 4.c](#). and will be summarized with descriptive statistics by regimen for baseline, postdose and change from baseline to postdose value for each part.

Overall ECG interpretation category (within normal limits, not clinically significant abnormal, clinically significant abnormal) is collected by eCRF according to the scheduled measurements. Shifts in ECG interpretation will be presented as cross-tabulations of numbers of subjects with normal, not clinically significant abnormal, and clinically significant abnormal ECG interpretation results and will include categories for missing and totals.

ECG parameters with markedly abnormal value (MAV) will be tabulated based on the value categories listed in [Appendix C](#).

Summary of Subjects with QTcF in various pre-defined categories will also be tabulated. Categories are listed in [Appendix C](#).

ECG data will be presented in the subject data listings.

7.11.5 Other Observations Related to Safety

All physical examination findings will be listed by study part, and regimen. Data on study drug overdose and interruption will be listed.

Data related to liver function test will be listed, including signs and symptoms, event history, test results and reports, and additional comments.

7.12 Interim Analysis

No formal interim analysis is planned for the study. However, Takeda will designate an external hepatologist as an independent assessor of any liver enzyme elevation in the study. Takeda will also designate a Pharmacovigilance physician who is not involved in the study conduct as a

sponsor liaison to participate and facilitate the safety communication between the external expert, the study site and Takeda.

7.13 Changes in the Statistical Analysis Plan

PK data will not be summarized for combining open-label and double blind parts of the study.

APPENDIX

Appendix A Criteria for Identification of Markedly Abnormal Laboratory Values Hematology—Criteria for Markedly Abnormal Values

Parameter	Unit	Low Abnormal	High Abnormal
Hemoglobin	SI	< 0.8 × LLN	> 1.2 × ULN
Hematocrit	SI	< 0.8 × LLN	> 1.2 × ULN
RBC count	SI	< 0.8 × LLN	> 1.2 × ULN
WBC count	SI	< 0.5 × LLN	> 1.5 × ULN
Platelet count	SI	< 75 × 10 ⁹ /L	> 600 × 10 ⁹ /L

LLN=lower limit of normal, RBC=red blood cell, ULN=upper limit of normal, WBC=white blood cell.

Serum Chemistry—Criteria for Markedly Abnormal Values

Parameter	Unit	Low Abnormal	High Abnormal
ALT	SI	--	> 3x ULN
AST	SI	--	> 3x ULN
GGT	SI	--	> 3x ULN
Alkaline phosphatase	SI	--	> 3x ULN
Total bilirubin	SI	--	> 34.2 μmol/L
Albumin	SI	< 25 g/L	--
Total protein	SI	< 0.8x LLN	> 1.2x ULN
Creatinine	SI	--	> 177 μmol/L
Blood urea nitrogen	SI	--	> 10.7 mmol/L
Sodium	SI	< 130 mmol/L	> 150 mmol/L
Potassium	SI	< 3.0 mmol/L	> 6.0 mmol/L
Creatine Kinase	SI	--	> 5x ULN
Glucose	SI	< 2.8 mmol/L	> 19.4 mmol/L
Chloride	SI	< 75 mmol/L	> 126 mmol/L
Triglycerides	SI	--	> 2.5x ULN
HDL-C	SI	--	--
LDL-C	SI	--	--
Total cholesterol	SI	--	> 7.72 mmol/L

ALT=alanine aminotransferase, AST=aspartate aminotransferase, GGT=γ-glutamyl transferase, LLN=lower limit of normal, ULN=upper limit of normal.

Urinalysis—Criteria for Markedly Abnormal Values

Parameter	Unit	Low Abnormal	High Abnormal
Blood	SI	--	$\geq 1+$
Glucose	SI	--	$\geq 1+$
Ketones	SI	--	$\geq 2+$
Casts	SI	--	$>1/1\text{pf}$
Microscopic RBCs*	SI	--	$\geq 5/\text{hpf}$
Microscopic WBC	SI	--	$\geq 20/\text{hpf}$
pH	SI	≤ 4	≥ 8
Protein	SI	--	$\geq 1+$
Specific Gravity	SI	--	--
Epithelial Cells	SI	--	--

Hpf=high power field.

*Markedly abnormal if repeated values both meet the criteria: ie, if two values are greater than or equal to 5/hpf within 30 days of one another.

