AEs will be presented in the listings, and TEAEs will be summarized. Clinical laboratory variables, vital sign, and ECG parameters will be summarized with descriptive statistics for Baseline, postdose, and change from Baseline to postdose values. The percentage of subjects with at least 1 postdose laboratory variable, vital sign, and ECG parameter that meet Takeda's predefined criteria will be summarized. Physical examination findings will be presented in the data listings. All summaries will be performed by regimen for each part separately and overall.

Sample Size Justification:

A total sample size of 64 subjects will be enrolled in this study. Sixteen subjects, 8 per regimen (TAK-491 40 mg and 80 mg) were randomized to the open-label part of the study. Forty-eight subjects, 16 per regimen (TAK-491 40 mg, 80 mg, and placebo) will be randomized to the double-blind part of the study. The sample size is considered sufficient for evaluation of safety, tolerability, and PK of each part of the study, and was not based on statistical power considerations.

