9.1.8 Procedures for Clinical Laboratory Samples

All samples will be collected in accordance with acceptable laboratory procedures. The approximate total volume of blood for the study is 243 mL. Laboratory samples will be taken following a minimum 8-hour overnight fast on the days stipulated in the Schedule of Study Procedures ([Appendix A](#)).

[Table 9.a](#) lists the tests that will be obtained for each laboratory specimen.

Table 9.a Clinical Laboratory Tests

Hematology	Serum Chemistry	Urinalysis
Red blood cells	Alanine aminotransferase	pH
White blood cells with differential (neutrophils, eosinophils, basophils, lymphocytes, monocytes)	Albumin	Specific gravity
Hemoglobin	Alkaline phosphatase	Protein
Hematocrit	Aspartate aminotransferase	Glucose
Platelets	Total bilirubin	Blood
	Total protein	Ketones
	Creatinine	Microscopic Analysis (a):
	Blood urea nitrogen	RBC/high power field WBC/high
	Creatine kinase	power field
	γ -Glutamyl transferase	Epithelial cells, casts etc.
	Potassium	
	Sodium	
	Glucose	
	Chloride	
	Triglycerides	
	HDL-C	
	LDL-C	
	Total cholesterol	

Diagnostic Screening:

Serum	Urine	Breath
HBsAg, anti-HCV, anti-HIV (b)	Drug screen, including amphetamines, barbiturates, benzodiazepines, cannabinoids, cocaine, opiates, and cotinine	Breath alcohol test
Additional Virology Tests:		
Anti-HBsAb, HBeAg, anti-HBeAb, anti-HBcAb, EBV VCA IgG, EBV VCA IgM, Anti-CMV IgG, and Anti-CMV IgM (c)		

Female Subjects only:

Serum hCG at Screening, Check-in, and Study Exit or Early Termination

EBV= Epstein-Barr virus viral capsid antigen, hCG=human chorionic gonadotropin, RBC=red blood cell, WBC=white blood cell.

(a) Microscopic analysis should be performed only if urine evaluations are abnormal.

(b) HBsAg, anti-HCV, and anti-HIV test results will be collected for all subjects.

(c) The results for the additional virology tests performed at Screening will be recorded in the (e)CRF for randomized subjects only.

The local laboratory will perform laboratory tests for hematology, serum chemistries, and urinalysis. The results of laboratory tests will be returned to the investigator, who is responsible for reviewing and filing these results.

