9.3.3 Day 1: Study Entrance

Study entrance will take place on Day 1. The following procedures will be performed and documented:

- Vital signs.
- PK urine collection.
- PK blood collection.
- Administration of study drug.
- AE assessment.
- Concomitant medications assessment.

Subjects will be administered study drug in the unit under the supervision of the investigator or designee, as described in Section 8.2. The procedure for documenting Screening failures is provided in Section 9.1.14.

9.3.4 Days 2 and 3

- Vital signs.
- PK urine collection.
- PK blood collection.
- AE assessment.
- Concomitant medications assessment.

9.3.5 Day 4

- Vital signs.
- Clinical laboratory tests.
- PK urine collection.
- PK blood collection.
- Administration of study drug.
- AE assessment.
- Concomitant medications assessment.

9.3.6 Days 5 and 6

- Vital signs.
- Administration of study drug.

- AE assessment.
- Concomitant medications assessment.

9.3.7 Days 7 through 10

- Vital signs.
- PK urine collection (Day 10 only).
- PK blood collection.
- Administration of study drug.
- AE assessment.
- Concomitant medications assessment.

9.3.8 Day 11

- Physical examination.
- Vital signs.
- Weight measurement.
- Clinical laboratory tests (including pregnancy test for all female subjects).
- 12-lead ECG.
- PK urine collection.
- PK blood collection.
- Concomitant medications assessment.
- AE assessment.

Subjects will be discharged from the clinic after the completion of all scheduled procedures and at the investigator's discretion.

For all subjects receiving study medication, the investigator must complete the End of Study CRF page.

9.3.9 Days 12 through 13

- Vital signs.
- PK blood collection.
- Concomitant medications assessment.
- AE assessment.

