- (g) Concurrent conditions are medical conditions that are present at Screening (time of informed consent).
- (h) Hematology, serum chemistries, and urinalysis tests. Blood and urine samples to be obtained before study drug dosing on Day 4. On Day 14, serum chemistry only; subjects with ALT/AST elevations on Day 11 and/or 14 will be followed-up every 5-7 days until resolution.
- (i) HBsAg, anti-HCV, anti-HIV, Anti-HBsAb, HBeAg, anti-HBeAb, anti-HBcAb, EBV VCA IgG, EBV VCA IgM, Anti-CMV IgG, and Anti-CMV IgM. HBsAg, anti-HCV, and anti-HIV test results will be collected for all subjects. The results for Anti-HBsAb, HBeAg, anti-HBeAb, anti-HBcAb, EBV VCA IgG, EBV VCA IgM, Anti-CMV IgG, and Anti-CMV IgM tests performed at Screening will be recorded in the (e)CRF for randomized subjects only.
- (j) Women of childbearing potential.
- (k) Study drug will be administered on Day 1 and Day 10 with 240 mL of water after a fast of at least 8 hours. On Day 1 and Day 10, subjects will also continue to fast for an additional 4 hours after dosing and subjects may consume water ad libitum with the exception of 1 hour before and 1 hour after drug administration. For Days 4 to 9, fasting is not required for dosing.
- (l) TAK-536 plasma PK: 6 mL blood samples will be collected on Day 1 at Predose (up to 15 minutes prior to dose [0 hour]) and at 0.5, 1, 2, 3, 4, 6, 8, 12, 16, 24, 36, 48, and 72 hours postdose. On Days 7, 8, and 9 at predose (up to 15 minutes prior to dose [0 hour]) and on Day 10 at predose (up to 15 minutes prior to dose [0 hour]) and at 0.5, 1, 2, 3, 4, 6, 8, 12, 16, 24, 36, 48, 72 hours postdose.
- (m) TAK-536 urine PK: urine will be collected starting on Day 1 at Predose (-12 to 0 hour) and at 0 to 2, 2 to 4, 4 to 8, 8 to 12, 12 to 24, 24 to 48, and 48 to 72 hours postdose and on Day 10 at 0 to 2, 2 to 4, 4 to 8, 8 to 12, 12 to 24, 24 to 48, and 48 to 72 hours postdose.
- (n) PTEs will be collected from the time of the informed consent to immediately prior to dosing on Day 1 of Period 1.
- (o) Subjects will be discharged from the clinic after completion of all scheduled procedures and at the investigator's discretion.

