(c) ICF must be signed before any study specific procedures are performed.

(d) Sitting blood pressure, pulse, respiration rate and oral temperature will be measured on Day -1, and on confinement days, vitals are to be measured pre-dose or upon morning rising. Vitals will be collected prior to the PK blood collection.

(e) Height (for calculation of BMI) will only be measured at Screening. Weight will be measured at Screening, Check-in (Day -1), and Study Exit or Early Termination Visit.

(f) Record all ongoing medications.

(g) Concurrent conditions are medical conditions that are present at Screening (time of informed consent).

(h) Hematology, serum chemistries, and urinalysis tests. Blood and urine samples to be obtained before study drug dosing on Day 4. On Day 14, serum chemistry only; subjects with ALT/AST elevations on Day 11 and/or 14 will be followed-up every 5-7 days until resolution.

(i) HBsAg, anti-HCV, anti-HIV, Anti-HBsAb, HBeAg, anti-HBeAb, anti-HBcAb, EBV VCA IgG, EBV VCA IgM, Anti-CMV IgG, and Anti-CMV IgM. HBsAg, anti-HCV, and anti-HIV test results will be collected for all subjects. The results for Anti-HBsAb, HBeAg, anti-HBeAb, anti-HBcAb, EBV VCA IgG, EBV VCA IgM, Anti-CMV IgG, and Anti-CMV IgM tests performed at Screening will be recorded in the (e)CRF for randomized subjects only.

(j) Women of childbearing potential.

(k) Study drug will be administered on Day 1 and Day 10 with 240 mL of water after a fast of at least 8 hours. On Day 1 and Day 10, subjects will also continue to fast for an additional 4 hours after dosing and subjects may consume water ad libitum with the exception of 1 hour before and 1 hour after drug administration. For Days 4 to 9, fasting is not required for dosing.

(l) TAK-536 plasma PK: 6 mL blood samples will be collected on Day 1 at Predose (up to 15 minutes prior to dose [0 hour]) and at 0.5, 1, 2, 3, 4, 6, 8, 12, 16, 24, 36, 48, and 72 hours postdose. On Days 7, 8, and 9 at predose (up to 15 minutes prior to dose [0 hour]) and on Day 10 at predose (up to 15 minutes prior to dose [0 hour]) and at 0.5, 1, 2, 3, 4, 6, 8, 12, 16, 24, 36, 48, 72 hours postdose.

(m) TAK-536 urine PK: urine will be collected starting on Day 1 at Predose (-12 to 0 hour) and at 0 to 2, 2 to 4, 4 to 8, 8 to 12, 12 to 24, 24 to 48, and 48 to 72 hours postdose and on Day 10 at 0 to 2, 2 to 4, 4 to 8, 8 to 12, 12 to 24, 24 to 48, and 48 to 72 hours postdose.

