7.11.2 Clinical Laboratory Evaluations

Clinical laboratory tests will be evaluated by central laboratory and presented using the International System of Units (SI) units unless otherwise stated. [Table 4.c](#) shows the scheduled measurements for clinical laboratory tests and [Table 7.d](#) shows a list of all clinical laboratory tests.

Table 7.d Clinical Laboratory Tests

Hematology	Serum Chemistry	Urinalysis
Red blood cells	Alanine aminotransferase	pH
White blood cells with differential (neutrophils, eosinophils, basophils, lymphocytes, monocytes)	Albumin	Specific gravity
Hemoglobin	Alkaline phosphatase	Protein
Hematocrit	Aspartate aminotransferase	Glucose
Platelets	Total bilirubin	Blood
	Total protein	Ketones
	Creatinine	Microscopic Analysis (a):
	Blood urea nitrogen	RBC/high power field
	Creatine kinase	WBC/high power field
	γ -Glutamyl transferase	Epithelial cells, casts etc.
	Potassium	
	Sodium	
	Glucose	
	Chloride	
	Triglycerides	
	HDL-C	
	LDL-C	
	Total cholesterol	
Diagnostic Screening:		
Serum	Urine	Breath
HBsAg, anti-HCV, anti-HIV (b) Additional Virology Tests: Anti-HBsAb, HBeAg, anti-HBeAb, anti-HBcAb, EBV VCA IgG, EBV VCA IgM, Anti-CMV IgG, and Anti-CMV IgM (c)	Drug screen, including amphetamines, barbiturates, benzodiazepines, cannabinoids, cocaine, opiates, and cotinine	Breath alcohol test
Female Subjects only:		
Serum hCG at Screening, Check-in, and Study Exit or Early Termination		

EBV= Epstein-Barr virus viral capsid antigen, hCG=human chorionic gonadotropin, RBC=red blood cell, WBC=white blood cell.

(a) Microscopic analysis should be performed only if urine evaluations are abnormal.

(b) HBsAg, anti-HCV, and anti-HIV test results will be collected for all subjects.

(c) The results for the additional virology tests performed at Screening will be recorded in the (e)CRF for randomized subjects only.

The following summaries will be provided for laboratory data by part and regimen:

- Baseline, postdose, and, change from baseline to postdose values for quantitative measurements.
- Number and percent of urine parameters results for categorical measurements.
- Number and percent of subjects with markedly abnormal value (MAV) which identified by the criteria in [Appendix A](#).
- Shift from baseline of high/low/normal values according to normal range criteria (baseline versus each post-baseline visit).

If a subject has multiple values within a particular visit window, the most abnormal result will be used for summary.

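### The SAP's two-value rule for microscopic urine RBCs cannot be met on scheduled samples by a finding that first appears after the Day 4 predose urinalysis, and the SAP does not require the pair to be postdose

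*SAP*

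**What the plan says.** **Criterion.** In the urinalysis table of SAP Appendix A, microscopic RBCs have a threshold of 5/hpf and an asterisk leading to this footnote: "Markedly abnormal if repeated values both meet the criteria: ie, if two values are greater than or equal to 5/hpf within 30 days" of each other. No other row in that appendix asks for a repeat. Dipstick blood, in the same table, is markedly abnormal at 1+ or more on one value.

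**Schedule.** Protocol Appendix A, footnote (h), defines the clinical laboratory tests and the Day 4 timing: "Hematology, serum chemistries, and urinalysis tests. Blood and urine samples to be obtained before study drug dosing on Day 4". It then limits the last visit: "On Day 14, serum chemistry only". SAP Table 4.c, footnote (h), has the same rule. Protocol Section 9.3.8 lists one laboratory set on Day 11. The remaining urinalyses are at Screening and Day -1, with an Early Termination set for subjects who stop early.

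**When a count exists.** Protocol Table 9.a, footnote (a): "Microscopic analysis should be performed only if urine evaluations are abnormal".

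**What is tabulated.** The protocol summary (Section 2.0) says: "The percentage of subjects with at least 1 postdose laboratory variable, vital sign, and ECG parameter that meet Takeda's predefined criteria will be summarized". SAP Section 7.11.2 promises "Number and percent of subjects with markedly abnormal value (MAV) which identified by the criteria in" Appendix A and does not say that the values must be postdose.

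**The concern.** A confirmation rule works only if a second sample is planned. Here the last urinalysis is the only one after repeated dosing begins, so a finding that arises during repeated dosing has no scheduled partner value. A zero in that row would reflect the sampling plan, but a reader could take it as evidence that nothing was seen, in the placebo arm as well as the active arms.

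The rule is also silent on baseline. A pair made up partly of a value taken before the first dose satisfies the footnote as written. The row can therefore count a subject whose finding was already present on Day -1, and omit one whose finding was new on Day 11. The secondary objective includes safety after multiple dosing, and this row contributes little to it as defined.

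**Working it through.** There is no published figure to reproduce. The check is to enumerate the scheduled pairs and apply the footnote.

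**Inputs.** Dosing on Day 1 and Days 4 to 10 (protocol Section 8.1.3). Urinalysis at Screening (Day -28 to -2), Day -1, Day 4 predose and Day 11. Rule: two values of at least 5/hpf, at most 30 days apart.

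**Step 1: doses after the Day 4 sample.** Days 4, 5, 6, 7, 8, 9 and 10 give 7 doses. With Day 1 the total is 8. So 7 of 8 doses are followed by one scheduled urinalysis.

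**Step 2: gaps.** There is no Day 0 (SAP Section 7.1.3), so elapsed day e = d - 1 for d of 1 or more, and e = d for negative d. Gap = e(later) - e(earlier).

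| Pair | Gap (days) | Within 30? |
|---|---|---|
| Screening, Day -1 | 1 to 27 | Always |
| Screening, Day 4 | 5 to 31 | If screened on Day -27 or later |
| Screening, Day 11 | 12 to 38 | If screened on Day -20 or later |
| Day -1, Day 4 | 3 - (-1) = 4 | Yes |
| Day -1, Day 11 | 10 - (-1) = 11 | Yes |
| Day 4, Day 11 | 10 - 3 = 7 | Yes |

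Only the last pair is wholly postdose.

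**Step 3: onset time, assuming the finding persists to Day 11.**

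| Onset | Scheduled positive values | RBC rule | Blood 1+ or more, postdose (if the dipstick is positive) |
|---|---|---|---|
| Before Screening | 4 | Can be met | Met |
| Between Screening and Day -1 | 3 | Can be met | Met |
| After the Day 1 dose, before the Day 4 sample | 2 (7 days apart) | Can be met | Met |
| After the Day 4 sample | 1 | Cannot be met | Met |

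**Step 4: illustrative records** (Screening, Day -1, Day 4, Day 11 in RBC/hpf; 0 stands for below 5 or microscopy not triggered).

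- (0, 0, 0, 50): not flagged. No second sample was scheduled.
- (0, 0, 50, 0): not flagged. The finding was not confirmed, so the rule is working as intended.
- (0, 0, 6, 6): flagged.
- (0, 6, 6, 0): flagged, although the finding predates dosing.
- (6, 6, 0, 0): flagged on the footnote alone, but has no postdose value and so falls outside the protocol summary's definition.

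The first and fourth records show the two defects.

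**The case against.** The strongest reply is that the rest of the plan covers most of this.

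- A reader might infer that haematuria arising on Days 4 to 10 cannot be flagged at all. The documents do not support that. Dipstick blood of 1+ or more flags on one value, so a Day 11 positive can be counted there. Because microscopy follows an abnormal urine evaluation, the residual gap is a Day 11 count of at least 5/hpf with dipstick blood below 1+ and no repeat. This stands.
- A reader might also infer that any pre-existing finding will be counted. The protocol summary asks for a postdose value, which excludes a Screening plus Day -1 pair. Inclusion criterion 6 limits out-of-range urinalysis at entry to results judged not clinically significant. Both points stand. But the SAP does not repeat the postdose condition, and SAP Section 7.13 declares no change on it. A Day -1 plus Day 4 pair contains one postdose value, so the protocol wording does not clearly settle that case.
- An unscheduled repeat could supply the second value. Protocol Section 9.1.8 refers to retesting of clinically significant abnormalities. That stands as a possibility only: no repeat urinalysis is mandated, and SAP Section 7.11.2 takes the most abnormal of several results in a visit window without saying whether a repeat still counts as a second value.
- The threshold belongs to the sponsor's predefined criteria, and requiring confirmation is a legitimate trade of sensitivity for specificity. This is fair, and it is a reason to keep the confirmed row.

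**Conclusion.** The point holds for one row of one descriptive table. On scheduled data, the microscopic-RBC criterion cannot be met by a finding that first appears after the Day 4 predose sample, a period that covers 7 of the 8 doses. Separately, the SAP leaves open whether a predose value may form half of the pair.

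This rests on two assumptions: that no unscheduled urinalysis is available, and that the footnote is programmed as written.

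The size is minor. It would be too strong to conclude that the secondary objective cannot be addressed. Safety also rests on adverse events, vital signs, ECGs, physical examination and the other laboratory tests. A Day 11 RBC result would still appear in the subject listings, the shift or categorical summaries (SAP Section 7.11.2) and the out-of-range summary (protocol Section 13.1.4). The PK endpoints are unaffected, and no formal test is planned.

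**What to change.** In SAP Appendix A and Section 7.11.2, for this trial:

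1. Keep the two-value row as the confirmed finding, and state that both values must be postdose.
2. Add a row for any single postdose value of at least 5/hpf in subjects whose baseline was below 5/hpf or did not trigger microscopy. Label a subject *unconfirmed* where no second value exists.
3. State that an unscheduled repeat within a visit window counts as a second value for the confirmed row.

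The cost is an amended footnote, an added row and a small programming change, with no new samples. The downside is that some sample-contamination findings will appear as unconfirmed, and the trial departs slightly from the sponsor's standard criterion. Showing both rows keeps the two kinds of finding apart.
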